The potential benefits of fevipiprant therapy need to be balanced against its potential risks. Potential side effects of fevipiprant include: increased heart rate, non-serious arrhythmia such as palpitations, headache, diarrhea, nausea, vomiting, nasopharyngitis, somnolence and dizziness. In humans, one major metabolite of fevipiprant has been identified which is formed by glucuronidation (acyl glucuronide) and partially binds to plasma proteins. In the literature, in vivo binding of acyl glucuronides to proteins has been reported to be associated with rare idiosyncratic drug reactions (IDRs), although a causal connection of protein adduction to IDRs remains uncertain (Regan et al 2010). There have been no IDRs observed with fevipiprant treatment in completed clinical trials as of January 2018. Taking fevipiprant at the doses used in this study with the cholesterol-lowering drug simvastatin has been shown to cause a small increase in the peak blood level of simvastatin.

The risk to patients in this trial will be minimized by compliance with the eligibility criteria and study procedures and close clinical monitoring.

Patients on doses of simvastatin > 20 mg, doses of atorvastatin >40 mg, doses of pravastatin >40 mg, or doses of pitavastatin > 2 mg per day (Elsby et al 2012; Deng et al 2008; Noé et al 2007; Kalliokoski and Niemi 2009), as well as patients on any statins with high creatine kinase (CK) levels (> 2 X ULN (upper limit of normal)) at screening will be excluded from the study. Patients on statin medication who are included in the study will have regular monitoring for relevant symptoms and be subject to discontinuation based on persistent myalgia and/or blood CK levels (Jacobson 2008). Cardiovascular risks will be monitored based on changes in vital signs, ECGs and biochemical parameters. Monitoring of liver function tests (LFT) and renal function will be conducted as described in Section 14 and Section 15, respectively, of this protocol. Surveillance of adverse events for identification of idiosyncratic drugs will be conducted.

Refer to the [QAW039 Investigator's Brochure] for further information about risks and benefits.

4 Population

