6.5.6 Electrocardiogram (ECG)

ECGs will be measured according to the assessment schedule in [Table 6-1](#). At Screening Visit, an ECG will be measured to test for eligibility for trial inclusion.

ECGs must be recorded according to the ECG investigator manual in the supine position to ensure a stable baseline. The preferred sequence of cardiovascular data collection during study visits is PRO collection first, followed by ECG, and then other study procedures. The Fridericia QT correction formula (QTcF) must be used for clinical decisions.

Single 12 lead ECGs are to be collected with ECG machines supplied by the core laboratory. Full details of all procedures relating to the ECG collection and reporting will be contained in an investigator manual to be provided to each investigator site.

The original trace will be sent electronically for central review directly from the ECG machine. Two ‘identical’ duplicate print-outs will be generated and kept at the investigator site as source

documentation and as back-up for submission to the central laboratory in case of problems with the electronic transmission. Each page of the ECG tracing must be labeled with study number (CQAW039A2323), subject initials (where this is allowed according to local regulations), subject number, date and time, and filed in the study site source documents.

For any ECGs with subject safety concerns, two additional ECGs must be performed to confirm the safety finding and copies forwarded to the central ECG laboratory for assessment. Clinically significant ECG findings prior to dosing with study drug must be discussed with the Novartis responsible person or designee.

Clinically significant abnormalities must be recorded on the relevant section of the medical history/Current medical conditions/AE CRF / e(CRF) page as appropriate.

In the event that the central cardiologist reports that an ECG is abnormal, then the investigator must comment as to whether the ECG abnormality is either clinically significant or clinically insignificant. If necessary a cardiologist may be consulted.

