

13 Appendix 1: Clinically notable laboratory values and vital signs

The central laboratory will flag laboratory values falling outside of the normal ranges on the central laboratory reports. Investigators are responsible for reviewing these abnormal values for clinical significance, signing the laboratory reports to indicate their review, and reporting values considered clinically significant in the appropriate electronic case report form (eCRF).

Any clinically significant abnormal laboratory value should be evaluated and followed-up by the investigator until normal or a cause for the abnormality is determined.

See Section 14 for specific liver event and laboratory test trigger definitions and follow-up requirements. See Section 15 for specific renal alert criteria and actions.

For electrocardiograms (ECGs), a notable QTc value is defined as a QTcF (Fridericia) interval of ≥ 450 msec for males or ≥ 460 msec for females – all such ECGs will be flagged by the Central contract research organization (CRO) and require assessment for clinical relevance and continuance of the patient by the Investigator.

14 Appendix 2: Liver event and Laboratory trigger Definitions and Follow-up Requirements

Table 14-1 Liver Event and Laboratory Trigger Definitions

[figure not shown]
	Definition/ threshold
LIVER LABORATORY TRIGGERS	
 3 x ULN < ALT / AST \leq 5 x ULN 1.5 x ULN < TBL \leq 2 x ULN
LIVER EVENTS	
 ALT or AST > 5 x ULN ALP > 2 x ULN (in the absence of known bone pathology) TBL > 2 x ULN (in the absence of known Gilbert syndrome) ALT or AST > 3 x ULN and INR > 1.5 Potential Hy's Law cases (defined as ALT or AST > 3 x ULN and TBL > 2 x ULN [mainly conjugated fraction] without notable increase in ALP to > 2 x ULN) Any clinical event of jaundice (or equivalent term) ALT or AST > 3 x ULN accompanied by (general) malaise, fatigue, abdominal pain, nausea, or vomiting, or rash with eosinophilia Any adverse event potentially indicative of a liver toxicity*

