2.8.4 Other safety data

2.8.4.1 ECG and cardiac imaging data

ECG measurements include heart rate, QT interval, RR interval, PR interval, QRS duration, and Fridericia's QTc (calculated as $QTcF = QT / 3\sqrt{RR}$ (in seconds), where $3\sqrt{}$ denotes the cube root).

ECG data measured more than 1 day after last intake of study drug are regarded as post treatment data and will not be summarized. All data will be included in the analyses regardless of rescue medication use.

Clinically relevant values

- The number and percentage of patients with newly occurring or worsening clinical relevant QTcF values (see [Table 2.8.1](#)) summarized at any time on treatment considering all post-baseline data from scheduled, unscheduled and premature discontinuation visits.

Table 2.8.1 Clinically relevant criteria for QTcF (Fridericia's formula)

ECG parameter (unit)	Clinically relevant range
Value considering newly occurring or worsening cases	
QTc (msec)	≥ 450 (male)
QTc (msec)	≥ 460 (female)
QTc (msec)	> 500 (both)
Change from baseline	
QTc	< 30
QTc	30 – 60
QTc	> 60

Clinically notable values

- A summary table will also be produced for number and percentage of subjects with notable QT and QTcF intervals (irrespective of the time point) using the following categories:
 - any treatment emergent (new) QTcF or QT interval ≥ 450 ms – 480 ms, > 480 ms – 500 ms or > 500 ms
 - QTcF or QT increase from baseline of ≥ 30 ms – < 60 ms, ≥ 60 ms
 - QTcF and QT increase from baseline of ≥ 30 ms plus QTcF interval ≥ 450 ms, > 480 ms or > 500 ms
 - QTcF increase from baseline of ≥ 60 ms plus QTcF interval ≥ 450 ms, > 480 ms or > 500 ms
- The number and percentage of subjects with noteworthy PR, QRS and HR interval changes will be reported using the below categories:
 - New PR > 200 ms to ≤ 220 ms; and > 220 ms
 - New QRS > 110 ms to ≤ 120 ms; and > 120 ms
 - PR increase $> 25\%$ to a value > 200 ms
 - QRS increase $> 25\%$ to a value > 120 ms
 - HR decrease $> 25\%$ to a HR < 50 bpm
 - HR increase $> 25\%$ to a HR > 100 bpm

Patients with notable post-baseline ECG values will be listed.

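### SAP 2.8.4.1: the 30 ms combined QT category, read literally, also requires uncorrected QT to rise, so a modest heart-rate increase removes true QTcF cases from that row; two other categories mix QT with QTcF

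*SAP*

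**What the plan says.** SAP 2.8.4.1 has two sets of QT summaries. The first, under clinically relevant values (Table 2.8.1), uses QTcF alone. It counts values (at least 450 ms in men, at least 460 ms in women, above 500 ms in either) and changes from baseline (under 30, 30 to 60, over 60 ms).

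The second, under clinically notable values, has four QT categories:

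1. New values: "any treatment emergent (new) QTcF or QT interval ≥ 450 ms – 480 ms", then above 480 to 500 ms and above 500 ms. Either interval qualifies.
2. Changes: "QTcF or QT increase from baseline of ≥ 30 ms" up to under 60 ms, then 60 ms or more. Either interval qualifies.
3. Combined, 30 ms: "QTcF and QT increase from baseline of ≥ 30 ms plus QTcF interval ≥ 450 ms", with further tiers above 480 and 500 ms. As written, both intervals must rise.
4. Combined, 60 ms: "QTcF increase from baseline of ≥ 60 ms plus QTcF interval ≥ 450 ms", with the same tiers. QTcF alone.

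Patients with notable post-baseline ECG values are also listed.

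The protocol works with the corrected interval. Section 6.5.6 states: "The Fridericia QT correction formula (QTcF) must be used for clinical decisions". In Appendix 1 (Section 13), "a notable QTc value is defined as a QTcF (Fridericia) interval of" at least 450 ms in men or 460 ms in women. Section 3.6 begins its list of possible harms: "Potential side effects of fevipiprant include: increased heart rate".

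**The concern.** The four categories follow three different rules, and the SAP gives no reason. The difference matters because uncorrected QT depends on heart rate: it shortens when the rate rises and lengthens when it falls.

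In category 3, a patient whose QTcF lengthens while heart rate rises can fail the uncorrected-QT condition and drop out. In categories 1 and 2, a patient with no change in QTcF can be counted because heart rate slowed.

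ECG is part of a stated secondary safety objective, so readers will compare these percentages between arms. At stake is the accuracy of one joint count, and the clarity of two other rows, for a drug whose listed potential side effects include a faster heart rate.

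**Working it through.** There is no stated figure to reproduce. The check applies the SAP's own correction to example patients.

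**Inputs.** From SAP 2.8.4.1: QTcF = QT / (RR in seconds)^(1/3), and the category limits. With RR = 60/HR, QT = QTcF × (60/HR)^(1/3). The heart rates and QTcF values below are assumptions.

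**Category 3, cases dropped.**

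| HR (bpm) | QTcF (ms) | QTcF rise | QT (ms) | QT rise | Category 3, literal | Category 3, QTcF only |
|---|---|---|---|---|---|---|
| 70 to 80 | 420 to 455 | 35 | 399.0 to 413.4 | 14.4 | no | yes |
| 60 to 75 | 410 to 450 | 40 | 410.0 to 417.7 | 7.7 | no | yes |
| 60 to 75 | 445 to 501 | 56 | 445.0 to 465.1 | 20.1 | no | yes, above-500 tier |
| 70 to 90 | 410 to 475 | 65 | 389.5 to 415.0 | 25.5 | no | yes |

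The last patient is recovered by category 4. The first three are not, because their QTcF rise is below 60 ms.

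**Heart-rate rise needed to drop a case.** The QT condition fails when the follow-up rate exceeds 60 × [QTcF₁ / (QT₀ + 30)]³. For baseline HR 60 and QTcF 410 to 450 ms: 60 × (450/440)³ = 64.2, a rise of 4.2 bpm. For baseline rates of 60 to 80 bpm and a final QTcF of 450 ms:

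- QTcF rise of 40 ms: about 4 bpm.
- QTcF rise of 50 ms: about 9 to 10 bpm.
- QTcF rise of 59 ms: about 13 to 16 bpm.

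At baseline rates above 60 bpm, a QTcF rise of exactly 30 ms fails with no rate change. At a constant 70 bpm, QT rises by only 30 × 0.950 = 28.5 ms.

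**Categories 1 and 2, cases added with QTcF constant.**

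- HR 70 to 55, QTcF 420 ms: QT 399.0 to 432.4 ms (+33.4), counted as a rise of 30 ms or more.
- HR 75 to 55, QTcF 410 ms: QT +41.5 ms, counted likewise.
- HR 70 to 50, QTcF 425 ms: QT 403.7 to 451.6 ms, counted as a new value of at least 450 ms.

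**Where the dropped patients still appear.** The first patient (QTcF 420 to 455 ms) is counted in the 30 to 60 ms row of Table 2.8.1, in category 2 and in category 1. A man also enters the 450 ms row of Table 2.8.1; a woman does not, because her limit there is 460 ms. No other row shows the rise and the resulting level together. Table 2.8.1 also has no 480 ms tier, so on the literal text a QTcF above 480 ms has its own QTcF-only count in that tier only when the rise is at least 60 ms.

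**Illustration under assumed inputs.** The simulation takes 60% women; baseline QTcF mean 418 ms (women) and 408 ms (men), SD 18, cut at the entry limits of 460 and 450 ms; HR mean 72, SD 10; within-patient change SD 15 ms and 9 bpm. Only the entry limits come from the protocol. Placebo has no shift.

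| Assumed drug effect | Row | QTcF only: active vs placebo | As written: active vs placebo |
|---|---|---|---|
| +10 ms, +5 bpm | rise ≥ 30 and QTcF ≥ 450 | 4.7% vs 1.1% | 2.0% vs 0.7% |
| +10 ms, +5 bpm | rise ≥ 30 | 9.1% vs 2.3% | 14.9% vs 11.2% |
| +10 ms, +10 bpm | rise ≥ 30 | 9.1% vs 2.3% | 11.1% vs 11.2% |
| 0 ms, +5 bpm | rise ≥ 30 | 2.3% vs 2.3% | 5.8% vs 11.2% |

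The literal category 3 keeps 59% of true joint cases with no shift, 42% at +10 ms and +5 bpm, and 24% at +10 ms and +10 bpm.

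**The case against.** The strongest defence is that the section as a whole conceals nothing. Table 2.8.1 counts QTcF values and changes without reference to QT, category 4 is on QTcF alone, categories 1 and 2 can never count fewer patients than QTcF would, and patients are listed. Heart-rate increases have their own row and pulse rate is summarised separately, so a heart-rate effect would be visible. This stands, and it confines the loss to one joint count.

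The wording may also be distributive. The lead-in to the list names both intervals, so category 3 could mean that each is reported in turn. No table shell is available to settle this. The ambiguity is real, but a programmer could follow either reading and the counts would differ.

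Nor does the protocol forbid the tabulation. Section 6.5.6 governs clinical decisions and Appendix 1 governs flagging for investigator review; neither limits what the SAP may summarise. This too stands: the point is one of analysis choice and internal consistency, not of a protocol breach.

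A reader might go further and infer that the plan hides QTcF prolongation, or that the error favours the drug. The documents do not support either. The dropped patients appear in other rows, and the either-interval rule dilutes a contrast rather than removing cases. Any net direction depends on a heart-rate effect, and in part on a QTcF effect, whose sizes the documents do not give.

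**Conclusion.** The point holds in a narrow form. Followed literally, category 3 undercounts the section's only joint count of a QTcF rise of 30 to under 60 ms reaching at least 450 ms or exceeding 480 or 500 ms, and it is inconsistent with category 4. Categories 1 and 2 mix heart-rate-driven QT changes into rows that a reader would take as QTcF findings, which can blur the contrast between arms.

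The mechanism follows from the SAP's own formula and needs no assumption beyond a change in heart rate. The size does need assumptions, and the simulated percentages are only illustrative. On those inputs, with the planned 669/3 = 223 patients per arm, the joint row in an active arm would show about 4 patients (223 × 2.0%) instead of about 10 (223 × 4.7%). Actual numbers would be smaller: SAP Section 4 records early termination by the sponsor with insufficient follow-up in most patients, and the protocol's assessment schedule has one scheduled ECG after screening.

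The table is descriptive, carries no test and does not touch the primary analysis. This is a minor point, worth making because it corrects a stated rule at almost no cost.

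**What to change.** In SAP 2.8.4.1, under clinically notable values:

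- Define the 30 ms combined category on QTcF alone, matching the 60 ms category.
- In the new-value and change categories, report QTcF and uncorrected QT in separate rows, so that QT does not enter any QTcF count.
- If the present wording was meant distributively, say so and show it in the table shell.

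The cost is SAP wording and one table shell. QTcF and QT are both already in the ECG data ("ECG measurements include heart rate, QT interval, RR interval, PR interval, QRS duration, and Fridericia's QTc"), so no new data or derivation is needed.

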2.8.4.2 Vital signs

Vital signs measurements include systolic and diastolic blood pressure (SBP and DBP), pulse rate, temperature, height and body weight. Vital signs data taken on or after the time of the first intake of study drug and until 7 days after the last intake of study drug are regarded as on-

treatment data. Vital signs data measured more than 7 days after last intake of study drug are regarded as post-treatment data and will not be summarized. All data will be included in the analyses regardless of rescue medication use.

The following analyses will be performed by treatment group:

- absolute on-treatment values and change from baseline summarized by parameter, and treatment group
- the number and percentage of patients with newly occurring or worsening notable vital signs on-treatment values (see [Table 2.8.2](#) for definition of notable values) summarized by parameter (except height), at any time on treatment considering all post-baseline data from scheduled, unscheduled and premature discontinuation visits
- Vital signs will also be summarized by clinically relevant categories:
 1. Pulse rate: < 40 bpm, 40 – 90 bpm, and > 90 bpm
 2. Systolic blood pressure: < 90 mm Hg, 90 – 140 mm Hg, and > 140 mm Hg
 3. Diastolic blood pressure: < 50 mm Hg, 50 – 90 mm Hg, and > 90 mm Hg.

The same approach as for notable laboratory values will be used to define a newly occurring notable vital sign value and a worsening notable vital sign value.

A listing of all patients with notable vital sign values and changes will be provided.

Table 2.8.2 Clinical notable criteria for vital signs

Vital sign parameter (unit)	Lower bound of clinically notable range	Upper bound of clinically notable range
Notable value considering newly occurring or worsening cases		
Systolic blood pressure (mmHg)	< 75	> 200
Diastolic blood pressure (mmHg)	< 40	> 115
Pulse rate (bpm)	< 40	> 130
Notable change from baseline		
Systolic blood pressure (mmHg)	≤ 90 and decrease from baseline by ≥ 20	≥ 180 and increase from baseline by ≥ 20
Diastolic blood pressure (mmHg)	≤ 50 and decrease from baseline by ≥ 15	≥ 105 and increase from baseline by ≥ 15
Pulse rate (bpm)	≤ 50 and decrease from baseline by ≥ 15	≥ 120 and increase from baseline by ≥ 15
Weight (kg)	Decrease ≥ 7% from baseline	Increase ≥ 7% from baseline

2.9 Pharmacokinetic endpoints

Not applicable.

2.10 PD and PK/PD analyses

Not applicable.

2.11 Patient-reported outcomes

PROs such as AQLQ+12 and ACQ-5 will be analysed as part of secondary endpoints.

2.12 Biomarkers

Not applicable.

2.13 Other Exploratory analyses

NA

2.14 Interim analysis

Not applicable.

3 Sample size calculation

The historical data (US MarketScan database) shown in [Table 3.1](#) indicates that the distribution of the total systemic corticosteroid dose in mg prednisone/prednisolone (or equivalent) across patients is not normal; rather the distribution is skewed; hence using a normal distribution assumption is not appropriate. In addition, the proportion of patients with 0 total systemic corticosteroid dose in mg prednisone/prednisolone (or equivalent) is quite high (>30%) therefore a transformation that could normalize the distribution is not feasible. As a consequence, a non-parametric method based on rank analysis will be used to analyze the primary end-point. The formula developed for the Wilcoxon-Mann-Whitney test adjusting for ties ([Zhao et al 2008](#)) has been used to estimate the sample size. A 1:1:1 randomization was used. There are four hypotheses to be tested for primary endpoint as stated in Section xxx.

Table 3.1 Frequency distribution of dose to display (non-normal) distribution of US MarketScan database

	HD ICS/LABA+LAMA 6 weeks		HD ICS/LABA+LTRA 6 weeks		HD ICS/LABA 6 weeks	
Outcomes	n=1562		n=7409		n=18471	
Dose Category (Count/%)						
0 (0mg)	533	34.1%	2901	39.2%	8211	44.5%
1 (>0 - 50 mg)	5	0.3%	20	0.3%	46	0.2%
2 (>50 - 100 mg)	25	1.6%	90	1.2%	214	1.2%
3 (>100 - 150 mg)	107	6.9%	595	8.0%	1376	7.4%
4 (>150 - 200 mg)	62	4.0%	358	4.8%	904	4.9%
5 (>200 - 250 mg)	90	5.8%	335	4.5%	808	4.4%
6 (>250 - 300 mg)	50	3.2%	313	4.2%	789	4.3%
7 (>300 - 350 mg)	40	2.6%	184	2.5%	426	2.3%
8 (>350 - 400 mg)	47	3.0%	216	2.9%	608	3.3%
9 (>400 - 450 mg)	44	2.8%	219	3.0%	519	2.8%
10 (>450 - 500 mg)	34	2.2%	181	2.4%	396	2.1%
11 (>500 - 550 mg)	24	1.5%	141	1.9%	308	1.7%
12 (>550 - 600 mg)	39	2.5%	221	3.0%	479	2.6%

13 (>600 - 650 mg)	19	1.2%	99	1.3%	237	1.3%
14 (>650 - 700 mg)	16	1.0%	80	1.1%	214	1.2%
15 (>700 - 750 mg)	28	1.8%	103	1.4%	252	1.4%
16 (>750 mg)	399	25.5%	1353	18.3%	2684	14.5%

[table 9_2](#) [Table 3.2](#) represents the selected scenario for the null and alternative hypothesis and the sample size under a 90% power and an overall alpha two sided of 5%. As we have two doses to test, the alpha considered for the sample size is 2.5% two sided.

Under the assumptions specified above and scenarios described in [Table 3.2](#), 134 patients per arm in the subpopulation with eosinophils count ≥ 250 cells/ μ l and 201 patients per arm in the overall population corresponding to a total sample size of 603 patients provide greater than 90% power for primary null hypotheses. Assuming 10% treatment discontinuation rate, a total of 669 patients are needed.

Table 3.2 Fevipiprant single dose EOS ≥ 250 cells/ μ l

alpha 2.5% power 90%	0- 50mg/ye ar	>50- 150 mg/yea r	>150- 300 mg/yea r	>300- 450 mg/yea r	>450- 600 mg/yea r	>600 mg/yea r	Hig h EoS	Full populatio n	+10 %
Placebo	42.7%	8.8%	13.5%	8.4%	6.6%	20.0%	-	-	-
Fevi	60.0%	15.0%	9.0%	3.0%	3.0%	10.0%	402	603	669

We have looked also at other possible distributions for both fevipiprant and placebo under a power of 80% or 90% and alpha 0.025 two sided. [table 9_3](#) [Table 3.3](#) provides other scenarios for the placebo and the Fevi group. Even if we deviate from the original scenario, other possible distributions provide still good power.

Table 3-3 Other scenario investigated for Fevipiprant single dose EOS ≥ 250 cells/ μ l

alpha 2.5%	0-50mg /year	>50-150 mg/year	>150- 300 mg/year	>300- 450 mg/year	>450- 600 mg/year	>600 mg/year	Power under the assumption of 134 pts per arm
Placebo	0.0%	10.0%	25.0%	25.0%	15.0%	25.0%	-
Scenario 1 Fevi	5.0%	25.0%	25.0%	20.0%	10.0%	15.0%	96%
alpha 2.5%	0- 50mg/year	>50-150 mg/year	>150- 300 mg/year	>300- 450 mg/year	>450- 600 mg/year	>600 mg/year	
Placebo	20.0%	5.0%	20.0%	10.0%	15.0%	30.0%	-
Scenario 2 Fevi	35.0%	20.0%	30.0%	5.0%	5.0%	5.0%	100%

alpha 2.5%	0- 50mg/year	>50-150 mg/year	>150- 300 mg/year	>300- 450 mg/year	>450- 600 mg/year	>600 mg/year	
Placebo	42.7%	8.8%	13.5%	8.4%	6.6%	20.0%	-
Scenario 3 Fevi	57.0%	18.0%	9.0%	3.0%	3.0%	10.0%	85%
Scenario 4 Fevi	55.0%	14.0%	14.0%	5.0%	3.0%	9.0%	75%
alpha 2.5%	0- 50mg/year	>50-150 mg/year	>150- 300 mg/year	>300- 450 mg/year	>450- 600 mg/year	>600 mg/year	
Placebo	0.0%	10.0%	25.0%	25.0%	15.0%	25.0%	-
Scenario 5 Fevi	5.0%	25.0%	20.0%	20.0%	12.0%	18.0%	82%

Based on clinical judgment different scenarios are considered in the above table

The following formula to calculate the sample size has been used (Zhao et al 2008):

$$N = \frac{(Z_{\alpha/2} + Z_{\beta})^2 (1 - \sum_{c=1}^D ((1-t)p_c + tq_c)^3)}{12t(1-t)(\sum_{c=2}^D p_c \sum_{d=1}^{c-1} q_d + 0.5 \sum_{c=1}^D p_c q_c - 0.5)^2}$$

Where

N is the total sample size for a 2 arm trial.

t is the randomization ratio

p_c are the % of patients in category c for the experiment arm

q_c are the % of patients in category c for the control arm

D is number of categories

4 Change to protocol specified analyses

The primary endpoint will be analyzed as specified in the protocol for the CSR and is detailed in this SAP. As the study is terminated early by sponsor, most of the patients don't have sufficient follow up and most of the data will not be matured enough do the analysis as defined in the protocol, due to that all secondary endpoints will be analyzed descriptively.

NA

5 Appendix

